4.1.3 Treatment Period (Day 1 to Day 29)

Subjects will continue to administer study agent twice daily, morning and evening, from Day 1 to Day 28 to all areas identified at the Baseline Visit and record each application in the e-diary. Study drug will be applied as a thin film to all involved areas twice daily, with at least 8 hours between applications. New areas that develop during the trial will be treated with study drug. Study drug will not be applied to the scalp, mouth, inside the nose, or eyes.

Subjects will be contacted by phone or video on Day 8 to assess for AEs, adherence with study agent application and prohibited medication use, and WI-NRS and e-diary completion. Compliance with study agent application will be emphasized.

Subjects will be present for in person visits on Day 15 and Day 29 when efficacy will be assessed using IGA, EASI, and TBSA. Safety assessments, including AEs, vital signs, urine pregnancy test, clinical laboratory tests, ECG, and local tolerability assessments will be conducted as per the SoA. The scores for WI-NRS will be reviewed. Adherence to study agent application will be confirmed by collecting and reviewing the e-diary at each visit and obtaining weight of the medication tubes at in person visits on Day 15 and Day 29/EOT. Standardized photographs of the same areas photographed at baseline will be obtained as per the SoA. If necessary, study procedures and visits may be modified in response to needs related to eg, coronavirus disease 2019 (COVID-19) (see [Section 8](#) and SoA [[Table 1](#)]).

Regardless if the lesions are decreased in area or resolved prior to the scheduled end of treatment (Day 29), the subject should continue to apply study drug twice daily for the entire treatment

period. New lesions that arise post-baseline will also be treated. Subjects will be instructed to bring all investigational product (used and unused tubes) to study visits on Day 15 and Day 29.

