Photography		X		X	X	Baseline photographs will be obtained prior to study drug application. The same regions will be photographed through the study under same conditions.
Randomization		X				
Local tolerability		X		X	X	At baseline, tolerability will be assessed pre-dose and 15 minutes after the first dose and also at Days 15 and 29.
Study drug application		X				1st dose of study drug will be applied by site staff and the subjects instructed on application. All subsequent application will be at home through evening dose on Day 28.
Dispense study medication, Instructions for Use, e-diary		X		[X]		Study drug will be weighed at the Baseline Visit, prior to first dose. Additional study drug may be dispensed on Day 15 if needed.
Instruct on WI-NRS tool		X	X	X		
Review e-diary, WI-NRS for compliance			X	X	X	The e-diary will be reviewed at each visit.
Collect and weigh study drug.				X	X	Study drug (used and unused tubes) will be collected and weighed at in person visits on Day 15 and Day 29. Study drug will be returned to subject at Day 15 and not returned to subject at Day 29.

AE=adverse event; BID = twice daily; D = Day; e-diary = electronic diary; EASI = Eczema Area and Severity Index; ECG= electrocardiogram; IGA = Investigator Global Assessment; PK = pharmacokinetics; TBSA = Total Body Surface Area; WI-NRS = Worst Itch Numeric Rating Scale.

^aETV: Early Termination Visit. All assessments scheduled for Day 29 will be conducted in event subject early terminates from study.

^bClinical labs: Complete blood count with differential, chemistry will be conducted at screening, baseline, Day 29. Urinalysis will be conducted at screening only. If the clinical laboratories were obtained within 14 days of baseline (Day 1), the screening labs will be used as the baseline labs and do not need to be repeated.

^cThe screening ECG will be used as the baseline ECG.

Teres Bio, Inc.
SAP for Protocol Number: TER-101-AD-201

^aPK blood draws should be done at least 4 hours after last study drug application. The date, time of last application will be recorded on electronic case report form page.
Avoid drawing PK samples through study drug application site.

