3.1 GENERAL STATISTICAL CONSIDERATIONS

Descriptive statistics (mean, standard deviation [Std Dev], median, minimum, and maximum) will be used for continuous variables; number and percentage of subjects will be used for discrete variables. In general, the last measurement prior to the first dose of study treatment will be used as the baseline value with exception of WI-NRS, where the score recorded on Day 1 describing the worst itch score 24 hours prior will be used as the baseline. Nominal visits will be used for by-visit summaries and analyses for safety evaluations (i.e., laboratory sampling, physical examinations, vital signs, and electrocardiogram). For efficacy evaluations of EASI, IGA, and TBSA, analysis visits will be used for by-visit summaries. Analysis visits are defined as below:

Analysis Visit*	Target Day	Range
Day 8	Day 8	Day 2 – Day 11
Day 15	Day 15	Day 12 – Day 21
Day 29	Day 29	≥Day 22

* If there are multiple observations in the range, then the record collected closest to the target day will be selected; if there are multiple observations that have equal distance from the target day, the latter one will be used.

All treatment group comparisons will be made at the 0.05 level using a two-sided hypothesis test, unless otherwise specified. Given the exploratory nature of this study, p-values from all significance tests will be reported without adjustment for multiplicity.

Summaries will be presented by each treatment group, ie, TER-101 2.75% ointment, Vehicle ointment.

All tabulations of summary statistics, graphical presentations, and statistical analyses will be performed using SAS[®] Version 9.4 or higher.

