3.2 ANALYSIS POPULATION AND DISPOSITION OF SUBJECTS

3.2.1 Data Sets Analyzed

For purposes of analysis, the following populations are defined

Population	Description
Efficacy analysis set (ES)	All randomized subjects who receive at least 1 application of the study treatment and have at least 1 post-baseline efficacy assessment. The treatment group as assigned (randomized to) will be used for analyses.
Per protocol efficacy analysis set (PPES)	All subjects in ES without major protocol deviations that impact the interpretation of the results. The treatment group for the first application will be used for analyses.
Safety analysis set (SS)	All randomized subjects who receive at least 1 application of the study treatment. If any TER-101 was applied, then the subject will be summarized under TER-101 treatment group.
PK analysis set (PKS)	All subjects in SS with at least 1 blood draw to measure TER-101.

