3.6.1 EASI Analyses

For each visit (baseline, Day 15, Day 29), the following analyses will be performed. All analyses will be based on the ES.

- Descriptive statistics (n, mean, Std Dev, median, minimum, and maximum) will be provided for the per-subject EASI total score (continuous), change from baseline, and percent change from baseline in EASI total score.
- Descriptive statistics (n, %) will be provided for the number and percentage of subjects who achieve EASI-50 (i.e., ≥50% reduction from baseline) and EAST-75 (i.e., ≥75%).

Descriptive statistics (n, mean, Std Dev, median, minimum, and maximum) will be provided for the per-subject EASI by region (head, trunk, upper extremity [UE], lower extremity [LE]), change from baseline, and percent change from baseline values. Treatment group comparisons

in percent change from baseline in EASI total score will be analyzed using a mixed model for repeated measures (MMRM). The model will include fixed effect for study treatment (TER-101 2.75%, vehicle), visit day (Day 15, Day 29), and treatment-by-visit interaction, with visit as the repeating factor, subject nested within the investigational site as a random effect, and baseline score as a covariate. The variance-covariance matrix will be assumed to be unstructured. If the procedure does not converge then the replacement of variance-covariance matrix will be explored in the order of Toeplitz, first-order autoregressive, compound symmetric. The treatment p-value (TER-101 2.75% vs. vehicle), treatment difference, and 95% confidence limits from the model will be presented for the percent change from baseline in EASI at Day 29. Similarly, the treatment difference (TER-101 2.75% vs. vehicle) and 95% confidence limits will be presented for Day 15 as well. Line graphs of least squares mean in percent change from baseline of EASI scores will be presented for Day 15 and Day 29. These treatment group comparisons will be repeated for the PPES.

The following sensitivity analyses will be conducted for the percent change from baseline in EASI total score at Day 29 to explore the impact of dropouts and missing data at Day 29.

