- Last value carried forward (LOCF): for timepoint Day 29, if missing, the last available post baseline EASI total score will be carried forward to the timepoint. After this imputation, an analysis of covariance (ANCOVA) will be used for analyzing the treatment effect at Day 29. The treatment group will be the fixed effect and baseline score will be the covariate. The treatment difference, 95% confidence limits, and p-value will be presented.
- Return to baseline: missing Day 29 value will be imputed based on the baseline value for the patient, with variance adjustment of the Day 29 EASI total score. That is, the missing data will be imputed with values from Normal distribution $N(\text{baseline}_i, \sigma_k^2)$; i = i th subject, where σ_k^2 is the variance estimate of treatment k at Day 29. Five hundred (500) imputation will be implemented. ANCOVA model will be used for each imputation. The results from all imputed datasets will be combined using Rubin's combination rule (PROC MIANALYZE).

In addition, the percent change from baseline in EASI scores and the absolute change from baseline in EASI total score by each region will be analyzed using the MMRM model, as described above. In each case, the treatment p-value (TER-101 2.75% vs. vehicle), treatment difference, and 95% confidence limits from the model, will be presented.

The effect of treatment on response rates (EASI-75, EASI-50) at each visit will be evaluated using a logistic generalized linear mixed model (GLMM) for binary data. The model will include fixed effect for treatment, visit and treatment-by-visit interaction, with subject nested within the investigational site as a random effect. The treatment p-value (TER-101 2.75% vs. vehicle), treatment odds ratio, and 95% confidence limits from the model, will be presented. [Note: In the event of model non-convergence, the response proportions will be analyzed using the Cochran-Mantel-Haenszel test, stratified by baseline IGA.] Bar charts of the response rates at Day 15 and Day 29 will be presented by treatment groups for each response rate (EASI-75, EASI-50).

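### Does it matter that SAP 3.1 ties the EASI, IGA and TBSA visit windows to summaries and does not expressly extend them to the models?

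*SAP*

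**What the plan says.** SAP Section 3.1 handles safety and efficacy visits in consecutive sentences. For safety: "Nominal visits will be used for by-visit summaries and analyses for safety evaluations". For the clinician-rated efficacy scores: "For efficacy evaluations of EASI, IGA, and TBSA, analysis visits will be used for by-visit summaries". The windows are Day 8 (Days 2 to 11), Day 15 (Days 12 to 21) and Day 29 (Day 22 onwards). The record nearest the target day is kept, and the later one if two are equally near.

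Protocol Section 4.1.3 schedules no efficacy scoring on Day 8: "Subjects will be contacted by phone or video on Day 8 to assess for AEs". By contrast, "Subjects will be present for in person visits on Day 15 and Day 29 when efficacy will be assessed using IGA, EASI, and TBSA". The early termination visit shares a column with Day 29 in the schedule of activities (SAP Section 2.1), and a footnote adds: "All assessments scheduled for Day 29 will be conducted in event subject early terminates from study".

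The primary MMRM in SAP Section 3.6.1 has "visit day (Day 15, Day 29), and treatment-by-visit interaction, with visit as the repeating factor". The TBSA and IGA models (Sections 3.6.4 and 3.6.2) have the same two visit levels. The EASI-50/75 model refers to each visit without listing levels. The efficacy set takes treated subjects who "have at least 1 post-baseline efficacy assessment" (Section 3.2.1).

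**The concern.** The safety sentence names analyses and the efficacy sentence does not. Read literally, the SAP never says which visit label feeds the efficacy models. The Day 8 row makes this concrete, because a score dated Days 2 to 11 can hardly come from anything but an early termination visit.

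Two outcomes are then conceivable. If the windows feed the models, that score is labelled Day 8, which is not a level of the EASI, IGA or TBSA model. A subject with no other score is in the efficacy set but adds nothing to the primary MMRM. If nominal labels feed the models, the shared column could turn the same score into a Day 29 value, 18 to 27 days early.

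These subjects are often treatment failures: Protocol Section 6.6.1 calls for the termination visit before rescue. If they leave unequally by arm, the two routes generally err in opposite directions. The topline result informs development planning (SAP Section 1.3), so the estimate should not hang on a programmer's choice.

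**Working it through.** **1. The plan's own figure.** SAP Section 1.2 plans about 60 randomized, 15% dropout and about 50 completers. 60 × 0.85 = 51, and 50 / 0.85 = 58.8, so 59. The figures agree. Expected withdrawals: 60 × 0.15 = 9.

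**2. Where each record goes.** Scheduled visits have a ±3 day allowance: Day 15 covers Days 12 to 18 and Day 29 covers Days 26 to 32. Both lie inside the analysis windows of the same name, so the choice of label is immaterial for subjects on schedule. Only early-termination scores differ:

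| Day of termination score | By window | By nominal column |
|---|---|---|
| 2–11 | Day 8 (not a model level) | Day 29 |
| 12–21 | Day 15 | Day 29 |
| 22 or later | Day 29 | Day 29 |

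**3. Which label the text supports.** Section 3.1 limits nominal visits to laboratory tests, physical examination, vital signs and ECG. Analysis visits are the only mapping it gives for EASI, IGA and TBSA. The windows bear the models' level names, and the nearest-to-target rule yields the single record per subject and visit that a repeated-measures model needs. Section 3.6.1 puts the descriptive statistics under the same Day 15 and Day 29 visits that the MMRM uses. The D29/ETV column lists procedures to perform; it is not an analysis rule.

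**4. How many subjects.** The documents do not give withdrawal timing. Assume 9 withdrawals, uniform over Days 2 to 28 (27 days, 10 of them in Days 2 to 11), all attending:
- Expected scores in Days 2 to 11: 9 × 10/27 = 3.3.
- Chance of at least one: 1 − (17/27)^9 = 0.984. If half attend: 1 − (22/27)^9 = 0.842.

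**5. What the plan does with those scores when windows apply.** They are outside the MMRM. The LOCF ANCOVA picks them up: "for timepoint Day 29, if missing, the last available post baseline EASI total score will be carried forward to the timepoint", with no limit by window. The return-to-baseline analysis keeps the subject but imputes around baseline. Protocol Section 9.7 requires missing Day 15 and Day 29 data to be counted by arm with reasons, and classified as informative or not before unblinding.

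**6. Size, by simulation.** The plan gives no SD, effect or correlation, so all of these are assumed: 30 per arm, SD 40, vehicle −30, effect −20 at Day 29, half the change by Day 8 and three quarters by Day 15, correlation 0.75, full attendance at termination, and three models in which poor scorers leave. The analysis is a two-visit unstructured MMRM with baseline covariate and no site term (2,000 runs, Monte Carlo SE at most 0.12). Average bias at Day 29 against complete data, in points (V toward vehicle, D toward drug):

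| Withdrawals, vehicle vs TER-101 | Windows as written | Day 15 window widened to Days 2–21 |
|---|---|---|
| 6 vs 3 | 0.7–1.8 V | 0.3 D to 0.5 V |
| 7 vs 2 | 1.3–2.8 V | 1.0 D to 0.3 V |
| 5 vs 5 (ten leave) | 0.0–0.1 V | 0.5–0.6 V |
| 3 vs 6 | 0.6–1.6 D | 0.6–1.3 V |
| Worst 9 of 60, arm ignored | 0.4–1.4 V | 0.1 D to 0.5 V |

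The sampling SD of the estimate is about 10 to 11. With 9 withdrawals and equal risk in both arms, a split of 7:2 or wider in either direction has probability 15%.

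**7. Does the wider window win?** Not clearly. Its RMS distance from the complete-data estimate is smaller (2.9–3.3 against 3.5–4.7). Its bias is larger at 5 vs 5, and its RMSE to the true effect is 0.0 to 0.4 higher when the worst scorers leave regardless of arm. A second simulation on the same assumptions (300 runs per case) gave RMS 2.9–3.7 against 3.4–4.5, but more bias at 5 vs 5 (0.6–0.9 against about 0.25) and at 3 vs 6 (1.2–1.8 against 0.8–1.2). A third (600 runs, one withdrawal model) put it at 2.1 D against 0.7 V at 7 vs 2. The ranking depends on the withdrawal pattern and on details of the simulation.

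**The case for a change.** The best case for a change sets the two labels against each other on the same data. In the main simulation, window and nominal estimates differ by 2.5 to 6.4 points in mean absolute terms (excluding the 3 vs 6 split), and the p<0.05 verdict differs in 10–19% of trials with a true effect. A simpler simulation gives mean gaps of about 2 to 9 points. In the earlier 1% study, 3 of 10 vehicle subjects with AD withdrew and none on TER-101 (Protocol Section 2.3). Protocol Section 9.7 also leaves missing-data detail to the SAP, and one sentence would settle the matter.

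The textual observation stands: Section 3.1 could have named the models, and the Day 8 row serves none of the models with listed visits. The magnitude argument does not carry over. Those gaps arise only if analysts apply to efficacy a label that Section 3.1 reserves for safety. The 10–19% also reflects a design with power near one half on the assumed inputs (0.49–0.51 with complete data at 7 vs 2), where small shifts often cross the threshold; with no true effect the figure is 3–7%. The earlier study enrolled more severe disease and gives no withdrawal timing.

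Two residual points are fair. If only half attend the termination visit, window-based bias at 7 vs 2 rises to 1.8–4.1 points toward vehicle. And the SAP writes its LOCF analysis for EASI percent change only, so an early IGA or TBSA score enters no model the SAP specifies. Whether the LOCF in Protocol Section 9.4.1 covers those endpoints is a separate question.

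**Conclusion.** This is a gap that analysts fill sensibly. The only visit mapping the SAP gives for EASI, IGA and TBSA is the window table, and it fits the models' visit levels. On that reading, a handful of early-termination scores (about 3 of 60 under even timing and full attendance) stay out of the primary MMRM. This is consistent with a two-visit model under the missing-at-random assumption in Protocol Section 9.4.1. For EASI, LOCF uses those scores, return-to-baseline gives a second view, and the missing-data table shows the imbalance by arm.

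The average cost is 0.0 to 2.8 points, usually toward vehicle when vehicle loses more subjects, against a sampling SD of 10 to 11. The trial is exploratory, has no statistical sample-size basis and makes no multiplicity adjustment. Moving early scores into Day 15 would exchange one small bias for another, and statisticians could reasonably differ on it. A clarifying sentence would do no harm, but the analysis does not depend on it. The sizes rest on assumed effect, SD, correlation, withdrawal timing and attendance, none of which the documents state; the reading of Section 3.1 does not rest on them.

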3.2 ANALYSIS POPULATION AND DISPOSITION OF SUBJECTS

3.2.1 Data Sets Analyzed

For purposes of analysis, the following populations are defined

Population	Description
Efficacy analysis set (ES)	All randomized subjects who receive at least 1 application of the study treatment and have at least 1 post-baseline efficacy assessment. The treatment group as assigned (randomized to) will be used for analyses.
Per protocol efficacy analysis set (PPES)	All subjects in ES without major protocol deviations that impact the interpretation of the results. The treatment group for the first application will be used for analyses.
Safety analysis set (SS)	All randomized subjects who receive at least 1 application of the study treatment. If any TER-101 was applied, then the subject will be summarized under TER-101 treatment group.
PK analysis set (PKS)	All subjects in SS with at least 1 blood draw to measure TER-101.

3.2.2 Protocol Deviations

Protocol deviations (eg, due to violations of inclusion or exclusion criteria, lack of study treatment compliance, or use of nonpermitted medication) will be identified and documented before database lock and unblinding. Number and percentage of subjects with deviations will be summarized by deviation categories. Major protocol deviations leading to exclusion of efficacy data from the analysis set PPES as described above will be listed.

3.2.3 Disposition of Subjects

The numbers of subjects screened (ie, signed informed consent), randomized, treated, and discontinued from treatment (by reason) or completed treatment, discontinued from study (by reason) or completed study will be summarized for each treatment group separately. Any mis-randomization or mis-treatment will also be described.

3.3 DEMOGRAPHIC AND OTHER BASELINE CHARACTERISTICS

Demographic and baseline characteristics will be summarized for the SS. Gender, race, and ethnicity will be summarized with number and percentage presented for each category. Age,

height, weight, body mass index (BMI) will be described with summary statistics (n, mean, Std Dev, median, minimum, and maximum).

3.4 MEDICAL HISTORY

All medical history and current ongoing medical history will be summarized separately by system organ class using the SS.

3.5 PRIOR/CONCOMITANT MEDICATIONS

The number and percentage of prior medications, and concomitant medications will be summarized by Anatomical Therapeutic Chemical (ATC) and preferred term (PT) separately using SS.

Medications taken any time prior to the first study treatment and stopped prior to the first study treatment are counted as prior medications. Those taken any time on or after the first application of study treatment or ongoing medication started prior to the first application of study treatment are counted as concomitant.

Subject will be counted only once within each classification. The same subject may contribute to two or more PTs within the same ATC classification.

3.6 EFFICACY ANALYSIS

All efficacy analyses and summaries will be performed on the ES by randomized treatment group. Additional analyses based on PPES will be specifically mentioned.

3.6.1 EASI Analyses

For each visit (baseline, Day 15, Day 29), the following analyses will be performed. All analyses will be based on the ES.

- Descriptive statistics (n, mean, Std Dev, median, minimum, and maximum) will be provided for the per-subject EASI total score (continuous), change from baseline, and percent change from baseline in EASI total score.
- Descriptive statistics (n, %) will be provided for the number and percentage of subjects who achieve EASI-50 (i.e., ≥50% reduction from baseline) and EAST-75 (i.e., ≥75%).

Descriptive statistics (n, mean, Std Dev, median, minimum, and maximum) will be provided for the per-subject EASI by region (head, trunk, upper extremity [UE], lower extremity [LE]), change from baseline, and percent change from baseline values. Treatment group comparisons

in percent change from baseline in EASI total score will be analyzed using a mixed model for repeated measures (MMRM). The model will include fixed effect for study treatment (TER-101 2.75%, vehicle), visit day (Day 15, Day 29), and treatment-by-visit interaction, with visit as the repeating factor, subject nested within the investigational site as a random effect, and baseline score as a covariate. The variance-covariance matrix will be assumed to be unstructured. If the procedure does not converge then the replacement of variance-covariance matrix will be explored in the order of Toeplitz, first-order autoregressive, compound symmetric. The treatment p-value (TER-101 2.75% vs. vehicle), treatment difference, and 95% confidence limits from the model will be presented for the percent change from baseline in EASI at Day 29. Similarly, the treatment difference (TER-101 2.75% vs. vehicle) and 95% confidence limits will be presented for Day 15 as well. Line graphs of least squares mean in percent change from baseline of EASI scores will be presented for Day 15 and Day 29. These treatment group comparisons will be repeated for the PPES.

The following sensitivity analyses will be conducted for the percent change from baseline in EASI total score at Day 29 to explore the impact of dropouts and missing data at Day 29.

- Last value carried forward (LOCF): for timepoint Day 29, if missing, the last available post baseline EASI total score will be carried forward to the timepoint. After this imputation, an analysis of covariance (ANCOVA) will be used for analyzing the treatment effect at Day 29. The treatment group will be the fixed effect and baseline score will be the covariate. The treatment difference, 95% confidence limits, and p-value will be presented.
- Return to baseline: missing Day 29 value will be imputed based on the baseline value for the patient, with variance adjustment of the Day 29 EASI total score. That is, the missing data will be imputed with values from Normal distribution $N(\text{baseline}_i, \sigma_k^2)$; i = i th subject, where σ_k^2 is the variance estimate of treatment k at Day 29. Five hundred (500) imputation will be implemented. ANCOVA model will be used for each imputation. The results from all imputed datasets will be combined using Rubin's combination rule (PROC MIANALYZE).

In addition, the percent change from baseline in EASI scores and the absolute change from baseline in EASI total score by each region will be analyzed using the MMRM model, as described above. In each case, the treatment p-value (TER-101 2.75% vs. vehicle), treatment difference, and 95% confidence limits from the model, will be presented.

The effect of treatment on response rates (EASI-75, EASI-50) at each visit will be evaluated using a logistic generalized linear mixed model (GLMM) for binary data. The model will include fixed effect for treatment, visit and treatment-by-visit interaction, with subject nested within the investigational site as a random effect. The treatment p-value (TER-101 2.75% vs. vehicle), treatment odds ratio, and 95% confidence limits from the model, will be presented. [Note: In the event of model non-convergence, the response proportions will be analyzed using the Cochran-Mantel-Haenszel test, stratified by baseline IGA.] Bar charts of the response rates at Day 15 and Day 29 will be presented by treatment groups for each response rate (EASI-75, EASI-50).

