6.4 Measures to Minimize Bias: Randomization and Blinding

6.4.1 Randomization

Study Using Precoded Randomization Provided to Site

On Day 1 (Baseline Visit), subjects will be assigned a unique number (randomization number) in ascending numerical order at each study site. The randomization number encodes the subject's assignment to receive study interventions, either TER-101 2.75% ointment or ointment vehicle according to the randomization schedule generated prior to the study by the Statistics Department at sponsor's designee. Each subject will be dispensed blinded study interventions, labeled with his/her unique randomization number, throughout the study.

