2.2 SUBJECTS

2.2.1 Number of Subjects

Approximately 60 adolescent and adult subjects (age 12 – 65) with mild to moderate AD will be enrolled across approximately 12 clinical research sites in the United States.

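### The nested subject term gives the EASI and WI-NRS mixed models no site effect; if sites differ and allocation is roughly balanced within site, the treatment standard error is too large and some power is lost

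*SAP*

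**What the plan says.** The primary mixed model in SAP 3.6.1 is listed term by term: "The model will include fixed effect for study treatment (TER-101 2.75%, vehicle), visit day (Day 15, Day 29), and treatment-by-visit interaction", then visit as the repeated factor, baseline score as covariate, and "subject nested within the investigational site as a random effect". On the repeated-visit covariance it says "The variance-covariance matrix will be assumed to be unstructured". The WI-NRS mixed model (SAP 3.6.3) uses the same nested random term, as do the EASI responder model (SAP 3.6.1) and the ordinal IGA model (SAP 3.6.2).

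Site appears in no other efficacy analysis:

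- The TBSA mixed model (SAP 3.6.4) and the protocol's own primary model (Protocol 9.4.6) have a plain subject random effect.
- For the LOCF ANCOVA, "The treatment group will be the fixed effect and baseline score will be the covariate".
- If the responder model does not converge, "the response proportions will be analyzed using the Cochran-Mantel-Haenszel test, stratified by baseline IGA".

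On allocation, Protocol 6.4.1 says that "subjects will be assigned a unique number (randomization number) in ascending numerical order at each study site", from a schedule prepared before the study. Neither document states whether the schedule is stratified by site or gives a block size. Subjects are "enrolled across approximately 12 clinical research sites in the United States" (SAP 2.2.1).

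**The concern.** The SAP added the nesting phrase to the protocol's model, and SAP Section 4 does not list it among the changes. A reader could take it to mean that site is accounted for in EASI and WI-NRS but not in TBSA. In fact it is accounted for in none of them.

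This matters only if sites differ. They may: EASI is graded by local assessors at about 12 sites. If treatment is also roughly balanced within site, site differences largely cancel from the treatment contrast, but a model without a site term still counts them as error. The confidence interval is then too wide and the test conservative. About 60 subjects were chosen without a power calculation, and the trial is meant to judge whether the drug merits further study, so precision that costs almost nothing is worth having.

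**Working it through.** **Inputs from the documents.** About 60 randomized, 15% dropout, about 50 completers (SAP 1.2); about 12 sites (SAP 2.2.1), so 60/12 = 5 per site; 1:1 allocation (SAP 2.3.2); two-sided 0.05 and SAS 9.4 or higher (SAP 3.1).

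**Assumed, because the documents give none.** Effect of 0.8 residual SD; total residual variance fixed at 1; site intraclass correlation (ICC) from 0 to 0.30; blocks of 4 within site; equal sites.

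**1. The plan's own figure.** 60 × 0.85 = 51 completers, and 50/0.85 = 58.8, so 59 to randomize. Both agree with the plan.

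**2. What the nested term contains.** Subject-within-site defines the same groups as subject. For 12 sites × 5 subjects × 2 visits, the random-effect designs for the two terms gave identical ZZ′ matrices, and the implied covariance between two subjects at one site was 0. A site intercept would make it the site variance. In SAS, subject(site) does not add a site term.

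The subject effect is also redundant. An unstructured 2 × 2 visit covariance has 3 parameters, which already fit the two variances and one covariance. A subject variance makes 4 parameters for 3 quantities.

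**3. Direction of the error.** With 51/2 = 25.5 per arm, the standard error without site is √(2/25.5) = 0.280. If allocation were exactly balanced in every site, the true value would be √(2(1 − ICC)/25.5):

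- ICC 0.2: √(1.6/25.5) = 0.250
- ICC 0.3: √(1.4/25.5) = 0.234

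The reported standard error would be too large by a factor 1/√(1 − ICC), that is 1.12 and 1.20. Sites of 5 with dropouts are not exactly balanced, so the real discrepancy is smaller. In the simulation below, mean reported standard error against actual SD of the estimate was 0.281 against 0.254 at ICC 0.2 (ratio 1.11) and 0.280 against 0.257 at ICC 0.3 (ratio 1.09).

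**4. Simulated size.** Day 29 comparison with baseline as covariate, 51 analysed, 2,000 trials per cell. The random-intercept analysis used REML with 51 − 3 − 12 + 1 = 37 degrees of freedom when all 12 sites are represented.

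| ICC | Type I, no site | Type I, random site | Power, no site | Power, random site | Gain (points) |
|---|---|---|---|---|---|
| 0 | 5.6% | 6.0% | 80.6% | 80.9% | 0.3 |
| 0.05 | 4.9% | 5.5% | 78.5% | 79.8% | 1.3 |
| 0.10 | 4.2% | 5.2% | 79.2% | 81.2% | 2.0 |
| 0.20 | 3.5% | 4.8% | 82.6% | 86.5% | 3.9 |
| 0.30 | 3.6% | 5.5% | 80.8% | 88.6% | 7.8 |

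Monte Carlo standard error is √(0.8 × 0.2/2000) = 0.9 points for power and √(0.05 × 0.95/2000) = 0.5 points for type I error. The range of 4 to 6 points quoted for ICC 0.2 allows for this noise; the run shown is at its lower end.

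A second simulation (3,000 trials per cell) gave power without and with the site intercept of 80% and 81% at ICC 0, 81% and 84% at 0.1, and 82% and 89% at 0.3. Type I error was 5.2% and 5.5%, 4.1% and 5.4%, and 3.1% and 5.0%.

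**5. Other conditions.**

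- Unequal sites (14 subjects down to 1), balanced within site: 82.5% to 86.7% at ICC 0.2, and 80.6% to 87.8% at 0.3.
- One central list: 78.8% to 83.6% at 0.2, and 78.5% to 85.6% at 0.3. Type I error without site stays near nominal (5.7% and 5.5%); with the intercept it was 6.4% and 6.2%.
- Fixed site effects at ICC 0: 76.4% against 80.6% without site (balanced within site), and 67.6% against 78.6% (central list).

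**The case against.** The strongest reply is that the planned test is valid. Its type I error is at or below about 5%, apart from simulation noise. The sample size makes no power claim, the analyses are declared exploratory, and the protocol never promised to adjust for site. All of that stands.

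Second, much of the gain is simply the removal of conservatism. In a separate simulation (1,500 trials per cell) with both tests set to the same type I error, power without and with site was 78.1% and 77.3% at ICC 0.05, 80.0% and 80.5% at 0.1, and 86.9% and 89.3% at 0.2. This also stands. Below an ICC of about 0.2 the practical benefit is an interval with closer to nominal coverage, not a sharper test.

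Third, site effects may be small. The endpoint is percent change from baseline, and the same evaluator is strongly recommended throughout (Protocol 1.1), so a constant proportional rater bias cancels. That lowers the plausible ICC but does not show it to be zero.

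Fourth, the simulations cover Day 29 alone, not the two-visit model, and do not use Kenward-Roger. That is a fair limit on the precision of the figures.

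A reader might go further and infer that omitting site inflates false positives, or that the analysis ignores a stratification factor. The documents support neither. The error runs in the conservative direction when allocation is balanced within site, and Protocol 6.4.1 describes numbering by site without stating stratification. Nor is it shown that the responder and IGA models should gain a site term. Neither was tested, and a second random effect in a binary model with about 25 completers per arm could raise the risk of non-convergence and so trigger the fallback test.

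**Conclusion.** The point holds as a modest efficiency loss. That the EASI, WI-NRS and TBSA mixed models contain no site effect follows from the SAP text alone. The size does not: it rests on the assumed ICC, effect, site sizes and blocking. Under those assumptions the power loss is nil at ICC 0, about 1 to 2 points at 0.05 to 0.1 (3 in the second run at 0.1), about 4 to 6 at 0.2 and about 7 to 8 at 0.3. Type I error without site is about 3 to 4% at 0.2 to 0.3. The conservatism depends on rough balance within site; under a central list type I error stays near 5%. It is a worthwhile improvement to make before unblinding, not a threat to the validity of the trial.

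**What to change.** In the mixed models of SAP 3.6.1 (EASI total and by region), 3.6.3 (WI-NRS) and 3.6.4 (TBSA), replace the subject random effect with: *investigational site as a random intercept; within-subject correlation modelled by the unstructured repeated-visit covariance; Kenward-Roger degrees of freedom*. This also removes the redundant subject term. Keep the site term even if its variance is estimated at zero, so that no data-dependent choice is needed.

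Add the same random site intercept to both Day 29 sensitivity ANCOVAs (LOCF and return to baseline), so that they differ from the primary model only in how missing data are handled.

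Leave the EASI responder model and the ordinal IGA model with a subject random effect only, and drop the nesting phrase there so that it does not suggest a site adjustment. Do not use fixed site effects: with about 5 subjects per site they cost power when sites do not differ. Record the change in SAP Section 4, and state there whether the schedule is stratified by site.

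The cost is SAP wording, a small change of code, one extra variance parameter, and a type I error near the nominal 5% instead of below it.
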